6.4.6.1 Six-week Postoperative Follow-Up Evaluation

- Clinical signs or symptoms of bleeding;
- Clinical signs or symptoms of embolism or thrombosis
- Reoperation and Re-Hospitalizations;
- Use of any blood modifiers, insulin, or blood sugar lowering medications or reversal drugs;
- Thromboembolism Assessment;
- DVT prophylaxis methods and duration; and
- Incidence of any complications/AEs.

6.4.6.2 24 Month Postoperative Follow-Up Evaluation (*for oncologic subjects only*)

- Assessment of Overall Survival: At 24 months, overall survival will be conducted. This may be completed by a medical records review, confirmation of an obituary, or other contact (phone call, email, letter, etc.). If there is no response after 3 documented attempts (one of which must be a certified letter), the subject will be considered lost to follow up.

6.4.7 *Evaluation Schedule*

Table 3 summarizes the acceptable visit windows for each evaluation time point.

Table 3. Visit Windows for Evaluations

Visit Type	Timing
Preoperative	Within 1 month (30days) before operative visit
Operative	Day 0
Postoperative	Within 24 hours postoperatively
Follow-Up: Discharge	Within 24 hours of hospital discharge or between 24 hours and 14 days postoperatively
Follow-Up: 6 Week	28-56 days postoperatively
Follow-Up: 24 Months*	23-25 months (700-760 days) postoperatively

*for oncologic subjects only

Table 4 summarizes the eCRFs that need to be completed at each time point.

Table 4. Completion of eCRFs

eCRF	Screening	Preoperative	Operative	Postoperative	Discharge	Follow-Up Visit(s)	Discontinuation
1: Subject Screening Form	X						
2: Preoperative Form		X					
3: Operative Form			X				
4: Postoperative Form				X			
5: Discharge Form					X		
6: Follow-Up Form						X	
7: Blood Modifiers Form	Where Applicable						
8: Laboratory Form		X		X			
9: Reoperation Form	Where Applicable						
10: Adverse Event Form	Where Applicable						
11: Discontinuation Form	Where Applicable						
12: Protocol Deviation Form	Where Applicable						
13: Equipment Calibration Form			X				

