6.6.2 Primary Efficacy Hypothesis

The primary efficacy hypothesis for this clinical investigation is that the proportion of subjects achieving hemostasis of the treated bleeding site at 7 minutes in the overall PerClot group is non-inferior to the proportion of subjects achieving hemostasis at 7 minutes in the overall control group.

$$H_0: P_{\text{PerClot}} < P_{\text{Control}} - \delta$$
$$H_a: P_{\text{PerClot}} \geq P_{\text{Control}} - \delta$$

where P_{PerClot} is the proportion of PerClot subjects achieving hemostasis at 7 minutes, P_{Control} is the proportion of control subjects achieving hemostasis of the treated bleeding site at 7 minutes, and δ is the non-inferiority margin, with $\delta = 0.10$.

The primary efficacy endpoint measure will also be reported by therapeutic area (subgroup): open elective cardiac, general, or urological surgical procedures. The proportion of PerClot and control subjects achieving hemostasis at 7 minutes will be reported, along with the absolute difference between the groups. A poolability analysis will also be performed on the therapeutic area subgroups. See Section 6.6.12. There are no labeling claims being sought out for this subgroup analysis.

Additionally, the number of subjects in whom hemostasis is achieved at 7 minutes, but have a re-bleed during the 5 minute observation period following the 7 minute assessment will be summarized. A sensitivity analysis of the endpoint will be conducted where all subjects that achieved hemostasis at 7 minutes, but did not maintain it for the 5 minutes following the assessment or any time after the observation period, will be counted as ‘failures’ in the analysis.

For subgroups, with an overall enrollment of 324 subjects in the study in the treatment and control cohorts, it is expected that there will be data on approximately 108 subjects in each subgroup. At a minimum, the study will enroll 50 subjects within a specific therapeutic area subgroup. At a maximum there will be 224 subjects in a single subgroup. A minimum of 50 subjects in each subgroup would lead to approximately 25 treatment subjects per subgroup. For a success rate of 92% (23/25), the distance from the observed rate of 92% to the lower bound of the two-sided 95% confidence interval is 18.0%. This planned minimum subgroup size would provide a reasonable degree of statistical precision for estimation of the treatment performance within subgroups.

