A sample size of 154 subjects in each group will provide $>$ approximately 80% power to reject the hypothesis of the inferiority of PerClot to the control by a 10% margin, using a one-sided 97.5% confidence interval. As the primary endpoint data is collected intraoperatively, no adjustment is made for attrition; however, the sample size was increased to account for the possibility of up to 5% loss within either group due to technical failures (i.e., contraindications, misdiagnosis, or intraoperative death prior to treatment, etc.), or subjects not treated according to randomization assignment, resulting in a sample size of 162 per arm to ensure $>$ 80% power in the overall sample including all three therapeutic areas. Thus, a total of 324 subjects will be enrolled across the three therapeutic areas. It is expected that there will be approximately equal numbers randomized within each of the three therapeutic areas, with an approximate 108 subjects in each therapeutic cohort.

A non-inferiority margin of 10% is consistent with the margins used in other controlled clinical trials involving hemostatic agents.^{24, 25} A non-inferiority margin $\delta = 0.10$ was chosen for this study because excluding a 10% difference between the treatments would be supportive of non-inferior performance of PerClot compared to the control.

6.6.6 *Blinded Sample Size Re-estimation*

In order to protect against lower than planned power due to misspecification of the assumed success rates, blinded sample size re-estimation will be performed.²⁶ The initial sample size

calculation will be repeated based on the observed pooled efficacy rate (i.e. the proportion of all subjects, regardless of randomization assignment, with 7 minute hemostatic success) rather than the initially assumed rate of 90%.

The re-estimation will be performed using the efficacy results of the first 20% and 50% of the minimum planned enrollment of 324(i.e. 64 and 162 subjects) pooled across randomized arm. The re-estimated sample size after 20% enrollment will provide an initial re-calibration of the sample size. The re-estimated sample size after 50% enrollment will determine the final sample size, which may be lower or higher than the re-estimated sample size after 20% enrollment.

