A comparison group of study subjects who are not treated with the investigational agent. The subjects in this group may receive no therapy, a different therapy, or a placebo.

Data

Factual information (such as measurements or statistics) used as a basis for reasoning, discussion, or calculation.

Death

All deaths are considered cardiac unless an unequivocal non-cardiac cause can be established.

Demographic Data

Refers to the characteristics of study participants, including sex, age, family medical history, and other characteristics relevant to the study in which they are enrolled.

Device

An instrument, apparatus, implement, machine, contrivance, implant, in vitro reagent, or other similar or related article, including any component, part or accessory, which is intended for use in the diagnosis, cure, treatment or prevention of disease. A device does not achieve its intended purpose through chemical action in the body and is not dependent upon being metabolized to achieve its purpose.

Device Accountability Records Log

Required documentation for material accountability, quantity used and left over, and date of disposal.

Device Malfunction

A product malfunction or user error, which caused an adverse event.

Dirty

A surgical procedure performed when an active infection is already present.

Discharge Form

A form designed to collect the required protocol information obtained at subject discharge.

Documentation

All forms of records that describe or document study methods, conduct and results, including any adverse events and actions taken.

eCRF

Electronic case report form.

Efficacy

A product's ability to produce beneficial effects on the duration or course of a disease. Efficacy is measured by evaluating the clinical and statistical results of clinical tests.

Embolism

The lodging of an embolus, a blockage-causing piece of material, inside a blood vessel. The embolus may be a blood clot, a fat globule, a bubble of air or other gas, or foreign material.

Enrollment

Enrollment in the study occurs when a patient meets the general inclusion/exclusion criteria, signs the informed consent form, meets the intra operative inclusion criteria and is randomized in the study.

eGFR

Estimated Glomerular Filtration Rate.

Food and Drug Administration (FDA)

Department within the United States Department of Health and Human Services. Enforces Food, Drug and Cosmetics Act and related federal public health laws. Grants IND, IDE, PMA, and NDA approvals.

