Follow-Up DRAFT Form
Form 6AForm completed by: _____
Date form completed: ____ / ____ / ____Subject Initials: Subject Number: Visit Date (DD/MMM/YYYY): / / Visit Type: 6 6-week follow-up 6 Unscheduled**FOLLOW-UP ASSESSMENT**

1. Does the subject have clinical signs or symptoms of bleeding?

1 Yes *If yes, please complete the Adverse Event Form.*
 0 No

2. Has the subject undergone a reoperation?

1 Yes *If yes, please complete the Reoperation Form.*
 0 No

3. Has the subject been re-hospitalized?

1 Yes *If yes, please complete the Adverse Event Form.*
 0 No

4. Use of any blood modifiers or reversal drugs? (This includes products known to affect bleeding, i.e., NSAIDs, ASA, omega-3 fatty acid supplements, herbal supplements.) *A list of blood modifiers can be found in the protocol Appendix L.*

1 Yes *If yes, please complete the Blood Modifiers/Blood Sugar Lowering Medications Form.*
 0 No

5. Use or administration of insulin or blood-sugar lowering medication? *A list of blood-sugar lowering medications can be found in the protocol Appendix K.*

1 Yes *If yes, please complete the Blood Modifiers / Insulin or Blood Sugar Lowering Medications Form.*
 0 No

6. Has the patient had any complications or adverse events since surgery?

1 Yes *If yes, please complete the Adverse Event Form.*
 0 No

Subject Initials: Subject Number:

CLINICAL SIGNS OR SYMPTOMS OF THROMBOEMBOLISM

7. Does the subject have clinical signs, symptoms, or events that may be associated with thromboembolism? *Check all that apply.*

A. Leg pain	 1 Yes	 0 No
B. Leg swelling	 1 Yes	 0 No
C. Chest pain	 1 Yes	 0 No
D. Shortness of breath	 1 Yes	 0 No
E. Transient orthostatic hypotension	 1 Yes	 0 No
F. Decreased level of consciousness presumed to be narcotic excess	 1 Yes	 0 No
G. Fainting spell	 1 Yes	 0 No
H. Hypoxia	 1 Yes	 0 No
I. Sudden death	 1 Yes	 0 No
J. Death without autopsy	 1 Yes	 0 No
K. Postoperative stroke due to patent foramen ovale	 1 Yes	 0 No

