Subject Initials: Subject Number: Visit Date (DD/MMM/YYYY): / / Visit Type: 6 24-month follow-up – oncology patients only**FOLLOW-UP ASSESSMENT**

1. Is the subject alive?

 1 Yes 0 No *If No, please complete the Adverse Event Form.* Unknown *If unknown, check all method of contact that apply.*

2. Confirmation methods utilized:

 1 Medical Record Review 2 Confirmation of Death via Obituary 3 Email/Letter 4 Phone Call 5 Lost to Follow up

The Subject is considered lost to follow up after three failed attempts to contact the subject by phone, letter, and/or email.

 6 Other: _____

Blood Modifiers / Insulin or Blood Sugar
Lowering Medications DRAFT Form
Form 8

 **CryoLife**®

Form completed by: _____

Date form completed: ____ / ____ / ____

PerClot® - The C.L.O.T. Investigation

Subject Initials:

Subject Number:

Visit Date (DD/MMM/YYYY): / / / /

Visit Type: 1 Preoperative

2 Operative

3 Postoperative

4 Discharge

5 6 week follow-up

6 Unscheduled

BLOOD MODIFIERS / INSULIN OR BLOOD SUGAR LOWERING MEDICATIONS / REVERSAL DRUGS

Record only relevant blood modifiers, i.e., Protamine, Aprotinin, etc. A list of blood modifiers and a list of blood sugar lowering medications can be found in the Protocol Appendices K & L.

1 None

Generic/Brand Name	Dose (with units)	Frequency*	Route of Admin**	Indication	Start Date and Time DD/MMM/YYYY: HH:MM (24-hour clock)	Stop Date and Time DD/MMM/YYYY: HH:MM (24-hour clock)	or Continuing
1. 					 /  /  /  /   :  	 /  /  /  /   :  	
2. 					 /  /  /  /   :  	 /  /  /  /   :  	

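### The glossary makes every death cardiac unless a non-cardiac cause is unequivocal; this does not suit a trial expected to be two-thirds general and urological surgery, and it contradicts the trial's own forms.

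*Protocol*

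**What the plan says.** Protocol Section 13 (Glossary, entry for Death) states: "All deaths are considered cardiac unless an unequivocal non-cardiac cause can be established". Nothing limits this to subjects having cardiac surgery.

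On the population, Protocol Section 6.6.5 says that "a total of 324 subjects will be enrolled across the three therapeutic areas", "with an approximate 108 subjects in each therapeutic cohort". Section 6.6.2 adds limits: "At a minimum, the study will enroll 50 subjects within a specific therapeutic area subgroup" and "At a maximum there will be 224 subjects in a single subgroup".

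On recording, Section 6.3.5 sends each death to the Adverse Event form and the Completion/Discontinuation form. In Appendix E, the Adverse Event form asks for a description, a CTCAE short name, an outcome (with a write-in for death from another cause) and the relationship to the device. The Completion/Discontinuation form asks for the probable cause of death. The Postoperative form (Question 8) and the 6-week Follow-Up form (Question 7) include sudden death and "Death without autopsy" in their thromboembolism checklists, and any ticked item requires an Adverse Event form.

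For oncologic subjects, Section 6.4.6.2 collects overall survival at 24 months: "This may be completed by a medical records review, confirmation of an obituary, or other contact". The 24-month form (Form 7) asks whether the subject is alive and instructs: "If No, please complete the Adverse Event Form".

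**The concern.** A cardiac default can be defended when all subjects are cardiac patients. Here two of the three therapeutic areas are liver, spleen and kidney surgery, and some subjects are followed for death to 24 months because they have cancer. The evidence accepted at 24 months may establish that the subject has died but will often not settle why. A rule that demands an unequivocal non-cardiac cause then supplies a cardiac one.

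What is at stake is the descriptive safety record. Embolism, thromboembolism, thrombosis and cancer recurrence or progression are named risks of the device and listed safety endpoints. A death that might belong to one of them, but cannot be proved to, would be described as cardiac when the honest description is that the cause is not known. A reader of the death narratives would also see cardiac deaths in nephrectomy or hepatectomy subjects for whom no cardiac finding exists.

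**Working it through.** **Population.** Inputs are the planned total of 324, three therapeutic areas and a minimum of 50 per area (Protocol Sections 6.6.2 and 6.6.5).

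- Expected per area: 324 / 3 = 108, which reproduces the plan's figure.
- Largest single area: 324 − 2 × 50 = 224, which reproduces the plan's figure.
- Expected general plus urological: 2 × 108 = 216, and 216 / 324 = 66.7%.
- Fewest general plus urological: 324 − 224 = 100, and 100 / 324 = 30.9%.
- Most general plus urological: 324 − 50 = 274, and 274 / 324 = 84.6%.

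A non-cardiac majority is therefore the expected case but is not guaranteed. Even at the lower limit, nearly a third of subjects fall outside cardiac surgery.

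**The rule against the forms.**

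1. *Death with no autopsy.* The postoperative and 6-week checklists treat it as a possible sign of thromboembolism. The glossary treats the same death as cardiac unless another cause is unequivocal. Take a nephrectomy subject who dies suddenly on day 10 without autopsy: the form points one way and the glossary the other.
2. *Standard of proof.* The Completion/Discontinuation form asks for the probable cause; the glossary accepts a non-cardiac cause only if it is unequivocal. A death that is probably, but not certainly, from pulmonary embolism gets a different answer under each.
3. *24-month death.* Form 7 has no field for cause and passes the death to the Adverse Event form, which needs a term and an outcome. Take a subject with liver metastases whose death at that visit is known only from an obituary. The only cause-of-death rule available to the site is the glossary default.

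**Is there another rule?** Neither document describes adjudication of cause of death. The committee in SAP Section 4.4.2 reads videos for hemostasis. The glossary sentence is the only instruction on the point.

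**What does not change.** Death is a listed event in its own right (Protocol Sections 6.1.3 and 6.6.4; SAP Section 4.4.4), so no death leaves that count. Embolism, thromboembolism and cancer progression have their own lines and are counted when diagnosed, whether or not the subject later dies. No endpoint or test uses a cardiac-death category.

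**The case against.** The strongest reply is that the sentence has no consequence. No table, test or form box contains the word cardiac as a death category, investigators already record a probable cause, and the protocol (Section 9.2) asks them to make every reasonable attempt to find the cause of an event. The checklists bring unexplained deaths forward as possible thromboembolism and do not hide them. The rule is also the same in both arms.

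Much of this stands, and it rules out three stronger readings that a reader might infer:

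- *That these deaths leave the counts of named device risks.* They do not: death is itself a named risk, and the other events are counted separately.
- *That a cardiac label leads to a grading of not related, and so lowers the count in the Fisher test of serious device-related events.* Nothing links the glossary entry to the relatedness judgement, which rests on timing and alternative causes. In a liver or kidney subject, a default cardiac cause is not obviously the underlying disease.
- *That a number of mislabelled deaths can be given, or a bias between arms shown.* A number would need the oncologic share, the mortality and the proportion of deaths without a settled cause. The documents give none of these, and they show no difference between arms.

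It is also true that correcting the rule would not move unexplained deaths into the embolism or cancer lines. Part of the gap at 24 months arises because that visit collects vital status only.

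What the reply does not answer is the contradiction. The forms have write-in fields for event term and cause, and the protocol's one rule for filling them disagrees with the forms that contain them.

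**Conclusion.** The concern holds as a defect in how cause of death is defined. The rule is trial-wide, does not suit the expected two-thirds of subjects outside cardiac surgery (216 of 324, permitted range 100 to 274), and conflicts with the thromboembolism checklists and the probable-cause field. If sites follow it, deaths of unproven cause acquire a cardiac cause or event term, and possible thromboembolic or cancer deaths become harder to see in the descriptive safety data.

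This is conditional on sites applying the glossary when they complete the forms; the documents do not show whether they would. The population range assumes a total of 324 and the stated limits per area. The number of affected deaths cannot be derived. Correcting the rule is worthwhile because the sentence serves no stated analysis, the contradiction is real and the change is small.

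**What to change.** Four changes:

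1. Replace the glossary entry. Suggested text: *Death: death from any cause. The investigator assigns the probable cause from the available records; where none can be established, the cause is recorded as undetermined.*
2. Add undetermined as an explicit choice where the Adverse Event and Completion/Discontinuation forms ask for a cause, and state that probable is the standard used.
3. State that the sudden-death and no-autopsy items on the postoperative and 6-week forms prompt an Adverse Event form and consideration of thromboembolism, and do not by themselves assign a cause.
4. In SAP Section 4.4.4, add a listing of deaths by cause, including undetermined, and by arm, covering 24-month oncologic deaths.

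The cost is one glossary entry, one response category, a clarifying note and one listing. Sample size, power and the primary analysis do not change. The drawback is that some deaths will be reported as undetermined, which reflects what is actually known about them.

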Appendix A: PerClot Instructions for Use

PerClot® Polysaccharide Hemostatic System Instructions for Use [L6421.014]

Caution: Investigational Device. Limited by United States Law to Investigational Use.

Read *Instructions for Use* prior to using this product.

Device Description

PerClot® Polysaccharide Hemostatic System (hereinafter referred to as PerClot) is a medical device composed of absorbable polysaccharide granules and delivery applicators. The granules are biocompatible, non-pyrogenic and derived from purified plant starch. The granules do not contain any human or animal components. PerClot granules have a molecular structure that rapidly absorbs water, forming a gelled adhesive matrix that provides a mechanical barrier to further bleeding and results in the accumulation of platelets, red blood cells, and coagulation proteins (thrombin, fibrinogen, etc.). One gram of PerClot absorbs at least 19 mL of water. The gelled adhesive matrix thus promotes the normal, physiological clotting cascade. PerClot granules are enzymatically degraded by alpha-amylase and glucoamylase and by macrophages. Based on preclinical studies, absorption normally requires several days and is dependent on the amount of material applied on the wound and the site of use.

Intended Use

The intended use for PerClot in this clinical investigation will be in surgical procedures as an adjunctive hemostatic device when control of capillary, venular, and arteriolar bleeding by pressure, ligature, and other conventional procedures is ineffective or impractical.

Contraindications

- Do not inject or place PerClot into blood vessels as potential for embolization and death may exist.
- Do not inject into bladder or ureteral lumen.
- Do not use in patients who have known sensitivity to starch or starch-derived materials.

Warnings

PerClot should not be used:

- In subjects undergoing a cardiac procedure in which there is no aortic anastomosis or aortotomy suture line to evaluate using the bleeding severity scale (i.e., not for treatment at the distal coronary artery bypass graft anastomosis);
- In subjects who have a clinically significant coagulation disorder or disease, defined as a platelet count <100,000 per microliter, an International Normalized Ratio >1.5, or a PTT more than 1.5 times outside the laboratory's normal reference range;
- In subjects who used corticosteroids (excluding inhalers, eye-drops, and dermatologic corticosteroids) within 6 weeks prior to surgery;
- In subjects who have undergone platelet receptor GP IIb/IIIa antagonist therapy less than 48 hours prior to surgery;

- In subjects who have been treated with an investigational product and have not completed the entire follow-up period for that investigational product;
- In subjects who are pregnant (as confirmed by a pregnancy test), planning on becoming pregnant during the follow-up period, or actively breast-feeding;
- In subjects with poor blood glucose control as per glycosylated hemoglobin > 9% and
- In subjects with an active or potential infection at the surgical site, or whose surgical wound is defined as wound classification CO (Contaminated) or D (Dirty or Infected) based upon the Centers for Disease Control and wound classification system.

NOTE: PerClot is predicted to activate Complement C3 because of its activity and fluid absorption capacity.

NOTE: The expected rate of absorption will vary depending on anatomic location. Elevated peri-operative blood glucose levels may also be associated with increased rate of wound infection. Elevated blood glucose levels in the immediate postoperative period may affect wound healing.

NOTE: The safety and effectiveness of PerClot have not been clinically evaluated in pediatric patients, on ophthalmic or neurologic tissues, or in laparoscopic cases.

NOTE: Once hemostasis is achieved, excess PerClot should be removed from the site of application by irrigation and aspiration. In an in vitro study where PerClot was agitated to ensure complete hydration, the average maximum swell capacity for each gram of PerClot in deionized water, saline, and blood were 59.7 mL, 27.1 mL, and 11.0 mL, respectively. Under these conditions the time to maximum swelling was 10 minutes. Dry, white PerClot should be removed. The possibility of the product interfering with normal function and/or causing compression necrosis of surrounding tissues due to swelling is reduced by removal of excess dry material.

Precautions

- PerClot is not recommended as a primary treatment for coagulation disorders.
- PerClot is intended to be used in a dry state. Contact with fluids prior to application will result in the loss of hemostatic properties.
- PerClot is not intended as a substitute for good surgical practice, and in particular, the proper use of conventional procedures (such as ligation) for hemostasis. Blood vessels with a diameter of $\geq 2\text{mm}$, suture line gaps $\geq 2\text{mm}$, and large needle holes $\geq 2\text{mm}$ must be ligated prior to PerClot application.
- Combined use of PerClot with other topical hemostatic agents has not been studied in controlled clinical trials.
- Remove excess PerClot granules once hemostasis is achieved. This is particularly important in and around the spinal cord and foramina of the bone since unsaturated granules may swell and compress the surrounding tissues.
- PerClot should not be mixed with methyl methacrylate or other acrylic adhesives as it may reduce the adhesive strength and compromise the attachment of prosthetic devices to bone tissue. Excess granules should be fully removed from bony surfaces by irrigation prior to the use of adhesives.
- As with other hemostatic agents, do not allow PerClot to enter into cell saver equipment, extracorporeal cardiopulmonary bypass circuits or autologous blood salvage circuits. Granules of PerClot or fragments of gelled PerClot may pass through 40 micron transfusion filters of blood salvaging systems.

Potential Adverse Events

Possible adverse events that could occur with the use of the investigational device may include, but are not limited to, the following:

- Adhesions or fibrosis;
- Anaphylaxis;

- Blockage of the bladder or ureteral lumen;
- Blockage of the bypass system;
- Cancer recurrence and/or progression;
- Compromised attachment of prosthetic devices to bone or tissue;
- Death;
- Embolism;
- Failure of deep or superficial wound healing;
- Failure to obtain hemostasis;
- Fever;
- Hemorrhage;
- Infection;
- Peri-operative hyperglycemia;
- Exacerbation of surgical procedure-associated adverse events;
- Swelling and compression of pressure-sensitive tissues and structures;
- Thromboembolism;
- Thrombosis; and
- Toxicity.

How Supplied

Contents of the PerClot package are supplied sterile for single-patient use only. These contents are sterilized by gamma irradiation and should not be re-sterilized. Discard any unused material from opened or damaged product.

PerClot should be stored between 0°C and 25°C.

PerClot should be used immediately after the package is opened.

Each box of PerClot supplied will contain five separate packages. Only two 5 gram bellows (packages) can be used per subject.

Preparation

1. Visually inspect the sealed packages. If either package has been previously opened or damaged, discard and replace with a new package.
2. Remove the applicator from the package.
3. Remove the granule dispenser (bellows) from its package. Remove the cap using a counter-clockwise turning motion (Fig. 1).
4. Connect the bellows firmly to the end of the applicator handle (Fig. 2). The system is now ready for use (Fig. 3). Pump the particle dispenser/bellows to deliver granules directly to the site of bleeding (Fig. 4).

[figure not shown]

Fig.1

Fig.2

Fig.3

Fig.4

Directions for Use

1. Perform conventional methods for hemostasis, including, but not limited to, pressure and ligature. Ligate any vessels \geq 2mm, suture line gaps \geq 2mm, and large needle holes \geq 2mm in diameter.
2. Confirm that there is bleeding.
3. Determine that there is bleeding which meets the predefined criteria. Remove all excess blood from the intended site by blotting, wiping, or suctioning. Identify and expose the source of bleeding of the wound. Ensure surface to which hemostat is being applied is dry and free from blood/fluid prior to application. Removing excess blood/fluid is critical to maximizing the hemostatic performance as it allows the PerClot granules direct contact with the site and source of active bleeding.
4. Pump the bellows bottle to deliver granules directly to the site of bleeding. Immediately apply a liberal amount of PerClot granules directly to the source of bleeding. Thoroughly cover the lesion with a layer of granules 3 to 4 mm in thickness. Extend the product application to approximately 0.5cm (or 5 mm) beyond the edge of the site of bleeding. The amount of application will depend upon the size of the bleeding site, contour of the bleeding site, and severity of bleeding. The amount of PerClot granules applied will increase with increasing size of the bleeding site and severity of bleeding.

NOTE: Do not apply more than the entire contents of up to two 5 gram bellows of PerClot implant material per subject.

5. The PerClot granules will help identify the source(s) of active bleeding; granules over source(s) of active bleeding will stain with blood. Additional PerClot granules should be applied to these area(s).
6. When managing deep wounds, the applicator tip must be as close to the source of the bleeding as possible without contacting blood.

CAUTION: Avoid contacting the applicator tip with blood as this may occlude the applicator. If this occurs, replace applicator tip, if available. If this occurs and a replacement tip is not available, use a stylus to reestablish the delivery pathway by inserting the stylus through the blocked area. Do not attempt to trim the applicator tip.

7. Gentle manual pressure will be applied until hemostasis is achieved. Gentle manual pressure will be applied until the first time point (5 minutes), and again between the first and second time points (7 minutes).

NOTE: Some materials such as standard gauze may adhere to the formed blood clot. Irrigation with saline before carefully removing the gauze is recommended. If standard gauze is adhered to the formed blood clot, the gauze should be fully saturated with saline, then gently and slowly peeled away. The use of a non-adhering substrate to apply pressure is recommended.

NOTE: To optimize the hemostatic performance of PerClot, it is important to ensure that the granules come into direct contact with the bleeding surface.

8. Once hemostasis is achieved, remove excess granules carefully and completely by gentle saline irrigation and aspiration.

NOTE: Following the application of PerClot for epicardial bleeding within the pericardial cavity and achievement of hemostasis, the pericardial cavity should be rinsed with up to 70cc of fluid per 1 gram of PerClot applied, which should be removed with suction, in order to ensure removal of excess particles. Observe the pericardial cavity for a minimum of 10 minutes after initial application for product swelling.

Product Information Disclosure

Handling and storage of this device by the user, as well as factors related to the patient, the patient's diagnosis, treatment, surgical procedures, and other matters beyond manufacturer's control, may directly or indirectly affect this device and the results obtained from its use. This device should not be used except on the order of a physician.

Disclaimer of Warranties, Limits of Liability

